Host genetics can contribute to gut communities, diet preference, inflammation and metabolism, and complex diseases such as Crohn's Disease, type II diabetes and obesity [8, 35]. For example, the NOD2 gene is a risk locus for irritable bowel disease (IBD), with 11 IBD genetic variations associated with a reduction in the *Roseburia* genus (which helps to produce butyrate) [36]. Suggestive links have also been found between the lactase non-persistence gene (LCT) variant and *Bifidobacterium* abundance [8].

In a recent study examining over 1514 Dutch individuals, 58 SNPs at 9 loci were associated with gut bacteria ($p < 5 \times 10^{-8}$, FDR < 12%). *Blautia* Genus (*Firmicutes* phylum) and *Methanobacteriaceae* members (*Euryarchaeota* phylum) had the strongest association with the host ($p < 5 \times 10^{-8}$), and are positively associated with Crohn's disease, obesity, lipid levels and BMI [37]. Genetic variants were identified in the *APOE* gene (lipid transfer) and the *PPAR* gene (fatty acid storage and glucose metabolism) [37]; both of which are predictor genes for $\dot{V}O_{2\max}$ trainability [6].

Studies have also found associations with the gut diversity and the Vitamin D receptor gene, GRIK 4 [38] and CD36 [9]. The latter two genes have been identified as possible predictor genes for $\dot{V}O_{2\max}$ trainability [6].

Exercise and the gut microbiome

Endurance exercise appears to increase alpha diversity, particularly members from the *Firmicutes* phylum [13]. Mice studies have demonstrated that a more diverse gut microbiota correlates with antioxidant enzyme activities (increased catalase and GPX activity) and hydration levels, which is associated with reduced fatigue and improved performance [13]. Human studies have found athletes to have greater gut diversity compared to the general population [11]. In a study of 40 male athletes and 40 comparators, the gut microbiota was significantly more diverse in the athletes, with a greater enrichment of pathways associated with *Akkermansia* bacteria, and production of short-chain fatty acids (e.g. butyrate and propionate) ($p < 0.001$) [11]. Butyrate was strongly associated with fiber intake, and propionate with protein intake [11].

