In a recent human cross-sectional study [12], $\dot{V}O_{2\text{peak}}$ was related to gut microbial diversity. Fourteen phyla (and 207 genera) were found across the 39 participants (age range 18-35 years). Those with a higher $\dot{V}O_{2\text{peak}}$ had a greater number of taxa (173 vs 153 for those with a lower $\dot{V}O_{2\text{peak}}$), with 20% of the variance attributed to $\dot{V}O_{2\text{peak}}$ independent cofounders, such as diet [12]. $\dot{V}O_{2\text{peak}}$ was significantly ($p < 0.05$) associated with butyrate-producing *Coprococcus*, *Roseburia*, *Adlercreutzia*, *Clostridiales*, *Lachnospiraceae* and *Erysipelotrichaceae* species [12]. Those with a higher $\dot{V}O_{2\text{peak}}$ had lower levels of lipopolysaccharide biosynthesis (which is related to inflammation), and higher levels of fatty-acid biosynthesis ($p = 0.046$) [12].

Furthermore, 6 weeks of aerobic training (30-60 minutes, 3x/week) increased the fecal concentration of acetate, propionate and butyrate concentrations in 32 sedentary adults, with changes in butyrate and acetate being BMI dependent (greater changes occurred in lean participants, $p < 0.05$) [39]. The butyrate regulating gene, butyral coA: Acetate CoA transferase (BCoAT), and the propionate regulating gene, methylmalonyl-CoA decarboxylase (mmdA), were positively related to the changes in short chain fatty acids following the exercise intervention ($p < 0.05$); with greater concentrations associated with a higher $\dot{V}O_{2\max}$, lean body mass and lower body fat at baseline (obese participants had double the concentration of BCoAT compared to lean participants) [39].

Diet (short chain fatty acids) and the gut microbiome

A high-fibre diet has shown to control appetite and weight; and reduce the risk of cardiovascular disease, colon cancer, irritable bowel disease and inflammatory bowel disease [40]. One of the gut's primary functions is fermentation of non-digestible carbohydrates (e.g. fiber) into short chain fatty acids (SCFA), including acetate, propionate, butyrate (ratio of 60:20:20 respectively); and secondary bile acids [13, 40]. The Firmicutes phylum mainly produces butyrate, whereas the Bacteroidetes phylum mainly produce acetate and propionate [40].

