Our gut microbiome is predetermined by host genetics that can be manipulated through numerous external factors, such as exercise and diet. Whilst host genetics and associated gut taxa increases susceptibility to various chronic diseases and overall fitness levels, the relationship between the gut microbiome and $\dot{V}O_{2max}$ trainability is unknown.

In addition to examining the gene predictor score for $\dot{V}O_{2max}$ trainability, our study will also investigate microbiota-related genes, host genes related to gut microbiome composition, and the genes involved with the gut-microbiota cross-talk. In conclusion, we hope to collect data to help understand if manipulation of the gut microbiome can improve the training response of individuals with a low gene predictor score for $\dot{V}O_{2max}$ trainability.

RESEARCH PLAN

Improving High Intensity Interval Training Response (IMPROVE-HIIT)

Overview

Improve HIIT will examine the association between the gene predictor score for $\dot{V}O_{2max}$ trainability the gut microbiome; and to investigate whether altering the gut microbiome via diet and training influences the $\dot{V}O_{2max}$ training response to HIIT.

Design

Improve HIIT is an 8-week randomised trial with two groups allocated to either: (1) HIIT plus placebo; or (2) HIIT plus prebiotic

Study Population

Consenting adults aged over 18 years.

Power Calculation (sample size justification)

The proposed project will be a pilot study. Considering financial resources, a sample size of 40 is possible. When using G*Power (download.cnet.com) ([52]), a sample size of 39 will achieve a medium effect size of 0.22 (using 6 predictors). This participant number is similar to a previous study examining if gut taxa is related to $\dot{V}O_{2max}$ levels [12]. A linear multiple regression model was used to include covariates that may contribute to the overall outcome (e.g. 6 predictors may include BMI, age, gender, initial $\dot{V}O_{2max}$, initial gut microbiome and cholesterol levels). Below are results of the power calculation:

F tests - Multiple Regression: Special (R^2 increase)

Analysis: A priori: Compute required sample size

Input:	Effect size f^2	= 0.22
	α err prob	= 0.05
	Power (1- β err prob)	= 0.8
	Numerator df	= 1
	Number of predictors	= 6
Output:	Noncentrality parameter λ	= 8.58
	Critical F	= 4.149097
	Denominator df	= 32
	Total sample size	= 39
	Actual power	= 0.8106

Recruitment

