The following table outlines the information to be collected.

Measure	Pre	Post
Cardiorespiratory Fitness		
VO _{2peak}	X	X
Resting blood pressure	X	X
Resting heart rate	X	X
Maximum heart rate	X	X
Gene Predictor Score		
Total number of variants that contribute to high or low response to training		
Diet History		
Food frequency questionnaire	X	X
24-hour diet recall	X	X
Gut Microbiota		
Diversity	X	X
Short chain fatty acid	X	X
Body Composition		
Weight	X	X

Body mass index	X	X
Waist circumference	X	X
Body fat percentage	X	X
Blood chemistry		
Total Cholesterol	X	X
HDL	X	X
LDL	X	X
Triglycerides	X	X
Glucose	X	X
DNA	X	
Family and Personal Medical History		
Family History of Cardiovascular Disease	X	
History of Illness or Injury	X	
Smoking status	X	
Medications	X	
Exercise habits	X	
CESD-R score	X	X

Statistical Analysis

Determining the association between the gene predictor score and the gut microbiome

Following on from the GWAS, a genetic predisposition score for each participant will be calculated to test for the cumulative effect of multiple alleles on $\dot{V}O_{2peak}$ training response and cardiovascular disease risk factors. Using the genetic variants identified from our PREDICT HIIT study (results yet to be published) and taking the approach used in Thomaes et al. (2011), '0' will be given for a homozygote for alleles associated with a low response to training, '1' for heterozygote for an allele associated with high response, and '2' for homozygotes of an allele associated with high response to training. The $\dot{V}O_{2max}$ scores and other covariates will be collated for each participant. Microba will provide gut bioinformatics for each participant (pre and post intervention). The butyrate production per participant will also be calculated as described above (pre and post intervention). This information (including average fibre intake per participant) will be analysed using SPSS statistical software (IBM SPSS Statistics).

Data will be tested for normality using a Shapiro-Wilk test. Where normality is not found, the Kruskal-Wallis test will be used for comparing between data sets.

To compare the mean OTUs (and other bioinformatics provided by 'Microba'), fibre intake and butyrate production for predicted low and high responders (e.g. gene predictor score), a one-way analysis of co-variance (ANCOVA) will be calculated (with age and sex as covariates).

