Investigating whether altering the gut microbiome via diet and training influences the $\dot{V}O_{2max}$ training response to HIIT

The change in $\dot{V}O_{2max}$ of each participant will be calculated. Low responders will be classified by a $\dot{V}O_{2peak}$ change of <100ml of O_2 /min, and high responders by a $\dot{V}O_{2peak}$ change of > 700ml in O_2 /min (following the intervention period).

To compare the mean change in OTUs, alpha diversity, fibre intake and butyrate production to $\dot{V}O_{2max}$ training response, a one-way analysis of co-variance (ANCOVA) will be calculated (with age, sex, baseline $\dot{V}O_{2max}$ as covariates).

A multiple regression analysis will be used to evaluate the role of possible predictors for change in $\dot{V}O_{2max}$. Predictors will be screened using a Spearman correlation matrix to find the top four significant variables to include in the multiple regression analysis (e.g. gene predictor score, sex, age, gender, BMI, fibre intake, OTUs, butyrate production, alpha diversity).

The above approach will also be used to compare changes in other biomarkers (e.g. blood tests, body fat percentage etc).

All statistical tests will be performed at a 5% significance level.

1. Montero, D. and C. Lundby, *Refuting the myth of non-response to exercise training: 'non-responders' do respond to higher dose of training*. JAP, 2017.
2. Mann, T., R. Lamberts, and M. Lambert, *High responders and low responders: factors associated with individual variation in response to standardized training*. Sports Med, 2014. **44**(8): p. 1113-1124.
3. Bouchard, C., et al., *Personalized preventive medicine: genetics and the response to regular exercise in preventive interventions*. Prog Cardiovasc Dis, 2015. **57**(4): p. 337-46.
4. Rankinen, T. and C. Bouchard, *Genetic predictors of exercise training response*. Current Cardiovascular Risk Reports, 2011. **5**(4): p. 368-372.
6. Williams, C., et al., *Genes to predict VO2max trainability: a systematic review*. BMC Genomics, 2017. **18**(Suppl 8:831).
7. Astorino, T. and M. Schubert, *Individual responses to completion of short-term and chronic interval training: a retrospective study*. PLoS One, 2014. **9**(5): p. e97638.

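### The ANCOVA linking gut change to observed VO2max response adjusts for age, sex and baseline VO2max but not for BMI or habitual fibre, which the protocol itself ties to butyrate

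*Protocol*

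**What the plan says.** Statistical Analysis in the protocol contains two gut ANCOVAs, each with a fixed covariate list.

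- The first, on the gene predictor score, compares OTUs, "fibre intake and butyrate production for predicted low and high responders" and is run "with age and sex as covariates".
- The second, on training response, takes the "mean change in OTUs, alpha diversity, fibre intake and butyrate production" and relates it to VO2max response "with age, sex, baseline" VO2max as the third covariate.

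BMI is in neither list. Fibre intake is one of the compared variables in both, so it adjusts nothing.

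Elsewhere the protocol connects both variables to this analysis:

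- Exercise and the gut microbiome (Background): a six-week aerobic training study is reported with "changes in butyrate and acetate being BMI dependent", and the athlete study with "Butyrate was strongly associated with fiber intake, and propionate with protein intake".
- Table 1: the agave inulin study reports butyrate positively associated with total fibre intake (p=0.005).
- Power Calculation: the "6 predictors may include BMI, age, gender" and other variables.
- Nutrition analysis: a 24-hour recall is collected before and after the intervention, with control for diet as a stated purpose.
- Statistical Analysis, multiple regression: BMI and fibre are example candidates for predicting VO2max change. Only the top four variables from a Spearman screen enter the model.

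**The concern.** The second ANCOVA does not compare the randomised arms. It compares gut change between people who turned out to respond differently to training. A characteristic that relates both to gut change and to response can create an association when neither affects the other.

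The protocol reports the gut side of that link for BMI (butyrate change) and for fibre (butyrate level). It treats the response side as plausible by listing both as candidate predictors of VO2max change. Body size also enters through the outcome scale: low and high responders are classified by change in absolute ml/min, while the Data Collection section reports VO2peak in mL/kg/min. For the same gain per kilogram, a heavier participant has the larger change in ml/min.

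At stake is how a positive result is read. A gut-response association from this model could be presented as evidence that microbiome change accompanies better trainability when body size or habitual diet accounts for part of it.

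**Working it through.** **The plan's own figure.** The power calculation is for a multiple regression, not for this ANCOVA, but it shows what extra covariates cost. Inputs from Power Calculation: f² = 0.22, α = 0.05, numerator df 1, 6 predictors, N = 39.

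- Denominator df = 39 − 6 − 1 = 32; λ = 0.22 × 39 = 8.58; critical F = 4.149; power = 0.8106. This matches the protocol.
- With 8 predictors: denominator df = 30, critical F = 4.171, power = 0.809. The required N stays at 39.

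**Can the other analysis supply the adjustment?** The regression retains BMI or fibre only if each ranks in the top four of the Spearman screen, so adjustment is possible but not guaranteed. It also models VO2max change, so it does not alter the ANCOVA results.

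**Size of a spurious association.** The documents give no correlations, so r² below is assumed. Let one factor explain a share r² of gut change and the same share of response, with no direct link between them. The induced correlation is √r² × √r² = r². With N = 40 and three unrelated covariates, Fisher's transformation gives

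P(reject) ≈ Φ(z − 1.96) + Φ(−z − 1.96), where z = atanh(r²) × √(40 − 3 − 3) = atanh(r²) × 5.831.

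| Assumed r² | z | Approximate P(reject) | Simulated, unadjusted | Simulated, adjusted |
|---|---|---|---|---|
| 5% | 0.292 | 6.0% | 5-6% | 4-6% |
| 10% | 0.585 | 9.0% | 6-9% | 4-6% |
| 20% | 1.182 | 21.9% | 11-22% | 4-6% |
| 30% | 1.805 | 43.8% | 19-45% | 4-6% |

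The approximation agrees with the upper end of each simulated range, where response is continuous and the factor is unrelated to baseline VO2max. The lower ends arise when the factor correlates −0.5 with baseline VO2max, which is already in the model, and response is split at the median.

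The effect of that correlation ρ can be written out: the induced partial correlation becomes (1 − ρ²)r² / (1 − ρ²r²). For r² = 20% and ρ = −0.5 this is 0.75 × 0.20 / (1 − 0.25 × 0.20) = 0.15 / 0.95 = 0.158. Then z = 0.93 and P(reject) is about 15%, instead of 22%.

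The median split stands in for the protocol's responder classes (below 100 and above 700 ml/min), whose sizes cannot be known in advance.

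**Cost in this model.** With one response term, residual df fall from 40 − 5 = 35 to 40 − 7 = 33.

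**The case against.** The strongest case on the other side has five parts.

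1. *The protocol does not call BMI or fibre common causes.* This stands. A reader might infer that they are known to drive butyrate and VO2max response. The text reports associations and one BMI-dependent training response. On the VO2max side it offers only example predictors, and nothing in it reports that fibre affects trainability. The reported BMI dependence concerns butyrate and acetate, not OTUs or alpha diversity. The point is therefore about possible confounding left unadjusted.
2. *The gene-score ANCOVA does not share the problem.* This stands. A reader might extend the point to it because its covariate list is shorter still. But BMI and fibre cannot cause genotype, and the Background says host genetics can contribute to diet preference and metabolism. Adjusting there could remove part of the association under test.
3. *Comparing fibre intake is not an error.* This stands. Participants are told to keep their usual diet, and comparing fibre across the groups is a legitimate check on that. What is missing is adjustment of the gut comparisons beside it.
4. *Baseline VO2max already carries some body-size information.* This stands in part. It lowers the rates, as shown above; with an assumed correlation of −0.7 they fall to about 10% and 18% at r² of 20% and 30%. Inflation is reduced, not removed.
5. *The multiple regression and the diet recall cover it.* This does not stand, because neither guarantees adjustment and the ANCOVA uses no diet data.

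**Conclusion.** The point holds for the ANCOVA of gut change on observed VO2max response. Its covariates are fixed in the protocol, the comparison is not randomised, and two variables that the protocol links to butyrate and names as candidate predictors of response are left out.

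The size depends wholly on assumption. If the shared r² is 5%, the false-positive rate is essentially nominal; at 10% the inflation is small; at 20-30% a nominal 5% test could reject 11-45% of the time without a true link. These rates assume one factor of equal strength on both sides, N = 40 and normal errors. They are not estimates for this trial.

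A reader might also infer that the randomised prebiotic-placebo comparison is biased. Nothing here supports that, since the point concerns only the association with observed response. In a 40-person pilot this is an inexpensive improvement to an exploratory analysis.

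**What to change.** In the second part of Statistical Analysis, add baseline BMI and baseline habitual dietary fibre to age, sex and baseline VO2max in the models for change in butyrate, OTUs and alpha diversity.

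- Take fibre from the diet data already collected and name the source in advance. The food frequency questionnaire aims at usual intake; the 24-hour recall is the instrument the protocol assigns to diet control.
- Use the baseline value, excluding the supplement. The prebiotic is itself fibre, so adjusting for total intake during the trial would remove part of the intervention effect.
- Keep the fibre-intake comparison as a separate diet check. Baseline fibre cannot adjust for diet change during the trial, so the check still has a purpose.
- Leave the gene-score ANCOVA unchanged.

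The cost is a change of wording and two degrees of freedom in a model of about 40 participants. No new data are needed.

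### Screening regression predictors by Spearman correlation and then testing them at 5% in the same 40 people raises the false-positive rate of the overall F test about three- to fivefold

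*Protocol*

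**What the plan says.** The relevant text is in the protocol's Statistical Analysis section, in the part on whether altering the gut microbiome influences the training response. A multiple regression is to assess possible predictors of change in VO2max. The selection rule is: "Predictors will be screened using a Spearman correlation matrix to find the top four significant variables to include in the multiple regression analysis". The candidates are given as "e.g. gene predictor score, sex, age, gender, BMI, fibre intake, OTUs, butyrate production, alpha diversity". The section closes with "All statistical tests will be performed at a 5% significance level", and the same approach is extended to the other biomarkers. No correction, hold-out sample or cross-validation is mentioned.

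The ANCOVA described just before the regression adjusts for age, sex and baseline VO2max.

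The Power Calculation section states "Considering financial resources, a sample size of 40 is possible" and bases the sample size on a regression: "A linear multiple regression model was used to include covariates that may contribute to the overall outcome". It adds that the "6 predictors may include BMI, age, gender, initial $\dot{V}O_{2max}$, initial gut microbiome and cholesterol levels".

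**The concern.** A variable that gets into the model because it correlated with the outcome in these data has already passed a test on these data. Ordinary p-values, the overall F test and R² assume that the predictors were fixed beforehand, so they are too favourable after such a screen. The screen also looks at one variable at a time and can discard a predictor that matters after adjustment.

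Three features of the text add to this:
- Baseline VO2max is not among the named candidates and nothing forces it in, although the neighbouring ANCOVA adjusts for it.
- Randomised arm is not named either.
- Sex and gender are listed as two candidates.

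At stake is which factors the trial reports as predictors of trainability, and how much variance it says they explain. The problem recurs for each biomarker to which the approach is applied.

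**Working it through.** **Inputs.** From the protocol: n = 40; α = 0.05; nine named candidates, or eight if sex and gender count once; at most four enter. Assumed, because the protocol does not give them: no candidate is related to the outcome, and candidates are independent or pairwise correlated 0.3. The rule can be read in two ways: (a) the four highest-ranked variables enter; (b) only variables with Spearman p < 0.05 enter, up to four.

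**Step 1: the protocol's own figure.** λ = f² × N = 0.22 × 39 = 8.58. Denominator df = 39 − 6 − 1 = 32. Critical F(1, 32) = 4.149097. Power from the noncentral F = 0.8106, an exact match (N = 38 gives 0.7998). The figure is correct for one coefficient tested in a model with six predictors. It makes no allowance for choosing predictors from the data.

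**Step 2: the screen alone.** The chance that at least one of k independent null candidates passes at 5% is 1 − 0.95^k. For k = 8 this is 0.337 (simulated 0.333); for k = 9 it is 0.370.

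**Step 3: screen plus regression.** Simulation with 5,000 replicates per row. Under reading (b), trials in which nothing passes count as not significant.

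| Candidates | Correlation | Overall F, (a) | Overall F, (b) | Any coefficient p < 0.05, (a) | Any coefficient p < 0.05, (b) |
|---|---|---|---|---|---|
| 8 | 0 | 0.187 | 0.244 | 0.309 | 0.236 |
| 8 | 0.3 | 0.142 | 0.213 | 0.255 | 0.187 |
| 9 | 0 | 0.231 | 0.282 | 0.336 | 0.273 |
| 9 | 0.3 | 0.168 | 0.235 | 0.271 | 0.200 |
| Four fixed in advance | 0 or 0.3 | 0.052–0.055 | – | 0.16–0.18 | – |

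The overall F test runs from 0.142/0.05 = 2.8 to 0.282/0.05 = 5.6 times nominal. The Monte Carlo standard error near 0.2 is √(0.2 × 0.8/5000) = 0.006. A separate set of runs gave 0.15–0.23 under (a) and 0.21–0.27 under (b), so about 15–27% is a fair summary. With the predictors fixed in advance the rate is back at about 5%, which identifies the screen as the cause.

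The right comparator for the any-coefficient columns is not 5%. Four independent prespecified tests give 1 − 0.95⁴ = 0.185.

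**Step 4: R².** With four prespecified null predictors the expected R² is 4/39 = 0.10. After selection by rank it averages about 0.15–0.17.

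**Step 5: would baseline VO2max survive if it were a candidate?** Nine independent candidates, 6,000 replicates. The true correlation with change is assumed, since the protocol gives none.

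| Assumed correlation | Kept under (a) | Kept under (b) |
|---|---|---|
| 0.2 | 69% | 22% |
| 0.3 | 84% | 43% |
| 0.4 | 95% | 69% |
| 0.5 | 99% | 88% |

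**The case against.** The study is called a pilot and the regression explores possible predictors. Arm is not a named candidate, so the selection does not bias a randomised comparison. An unseen statistical analysis plan might add validation or an exploratory label. The first two facts lower the severity. The last does not remove the point, because the protocol itself fixes the rule and a plan that follows it inherits the error.

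On one measure the excess is small. If only screen-significant variables enter, the chance of at least one coefficient with p < 0.05 is about 0.19–0.26, against about 0.18 for four fixed predictors, and in roughly two thirds of null trials nothing enters at all. This stands. However, with eight candidates 48–65% of the noise variables that do enter show p < 0.05.

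A reader might also infer more than the text supports:
- **That every error rate quadruples.** Only the overall F test rises by about that factor. Under entry by rank with eight candidates, the per-coefficient rate is 0.08–0.10, about 1.6–2 times nominal.
- **That far larger inflation is to be expected because the list is open.** Long lists do give more, but the protocol states no such number, and baseline, post and change versions of one variable are not independent.
- **That a fixed six-predictor model was powered and then abandoned.** The Power Calculation section only says what the six may include. What holds is that at most four selected predictors is a different analysis from six.
- **That baseline VO2max and arm are excluded.** The list gives examples only. What holds is that nothing forces them in.
- **That the effect of arm would be adjusted away.** Arm is not named, and the protocol does not say whether the gut variables are baseline, post or change values. At most the mediated part would be lost.

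**Conclusion.** The point holds and should be fixed; it is not critical. Following the protocol as written, the overall F test is falsely significant in about 15–27% of null trials, about 3–5 times nominal. With entry by rank, R² is inflated by about half or more (0.15–0.17 against 0.10), and the chance of some significant coefficient is about 0.27–0.34 against 0.18. These sizes rest on a global null, eight or nine candidates, independence or a correlation of 0.3, and the two readings of the rule. They are not protocol figures.

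Separately, the regression guarantees adjustment for neither baseline VO2max nor arm, which sits badly with the ANCOVA beside it. The protocol's power figure is arithmetically right but does not describe a model chosen from the data.

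**What to change.** Change the regression paragraph of the protocol's Statistical Analysis section:
- Delete the Spearman screen.
- Prespecify a small model for change in VO2peak with arm, baseline VO2peak, age, sex (listed once) and gene predictor score.
- Test further candidates (BMI, fibre intake, gut measures) one at a time in addition to this model, with false-discovery-rate control. Use baseline values only whenever arm is in the model.
- Label these predictor analyses, and the same approach for the other biomarkers, as exploratory.

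Prespecification restores the 5% level of the overall F test. It does not correct for reading several coefficients: five independent tests at 5% still give 1 − 0.95⁵ = 0.23, which is a further reason for the exploratory label.

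The cost is a wording change and no new data. The small downside is that fewer variables are examined jointly.
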